9.1 Study design

This study has a cohort design including nested case–control analyses.

Cohorts of first-time users of either rivaroxaban or comparators will be identified using the date of first prescription (index date) of the respective drug (index drug) (Figure 1).

A patient will be considered eligible to enter the study cohort as a first-time user of rivaroxaban or a first-time user of “standard of care” when he or she has a first prescription of the drug recorded during the enrolment period. In the UK, for VTE prevention, DVT/PE treatment and SPAF, standard of care is treatment with the most widely used vitamin K antagonist, warfarin, and for the secondary prevention of ACS, standard of care is antiplatelet drug(s) such as low-dose acetylsalicylic acid, clopidogrel, dipyridamole, prasugrel, ticlopidine and ticagrelor.

Patients who have any record of being prescribed their index drug prior to the enrolment period or who qualify as members of both cohorts on the same day, will be excluded. If a patient qualifies as first-time user of both rivaroxaban and “standard of care” comparison drug during the enrolment period, she/he will be assigned to the cohort of drug first prescribed during the enrolment period, with the date of this prescription being the index date.

Many patients with ACS have a history of ischaemic heart disease for which platelet inhibition is standard treatment, and thus exclusion of patients with prior use of platelet inhibitors risks excluding a majority of typical ACS patients. Therefore, those who have been using one or more platelet inhibitors will remain eligible to enter the study.

Standard of care for ACS patients is combination therapy, and as such cohort assignment will be based on first use of rivaroxaban (in combination with aspirin or clopidogrel, or multi-antiplatelet therapy), or use of aspirin and clopidogrel and/or other antiplatelet medications.

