Study subjects for DVT/PE treatment and SPAF, where the comparator is warfarin, will be categorized as naïve or non-naïve patients according to their previous use of any anticoagulant/comparator drugs (Figure 1). Naïve patients will be those without a previous prescription recorded before the index date. Non-naïve patients will be those with one or more relevant prescriptions recorded before the index date. Ascertainment of naïve/non-naïve status will also be confirmed by Read Code in addition to Drug Codes, e.g. Read Codes for warfarin monitoring, INR values >2, as this may be recorded in the absence of a Drug Code for warfarin.

Non-naïve patients will be further subdivided into recent switchers (patients exposed to the other anticoagulant/comparator in the 6 months prior to the index date) and distant switchers (patients exposed to the other anticoagulant/comparator more than 6 months prior to the index date).

[figure not shown]

Figure 1 Subdivision of study cohorts for DVT/PE treatment and SPAF.

Data collected for comparison of cohorts is described in [Section 9.3](#). The characteristics of the two study cohorts in the first year and subsequent years of the enrolment period will be compared.

Strengths of the study pertaining to the research question include:

- It uses observational data from routine clinical practice with no selection and no possibility to influence prescribing behaviour.
- Manual review of free text comments, questionnaires sent to primary care practitioners (PCPs) and cross-validation with hospital episode statistics (HES) in a subgroup of practices are possible, allowing for robust validation of outcomes.
- THIN is a well-validated resource for pharmacoepidemiology research (see [Section 9.2](#)).

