9.3 Variables

9.3.1 Patient characteristics and drug utilization

The following variables, including risk factors/potential confounders for the outcomes under study, will be collected for comparison between the two cohorts:

- age and sex distribution at index date; 
- dose of index drug at index date and duration of treatment (including pack size); 
- diagnosis associated with the prescribing of the index drug; 
- proportion of patients defined as naïve, non-naïve, recent switchers and distant switchers; 

- type and duration of other anticoagulant use before the index date among the non-naïve group; ✓
- number of pregnant women at index date; ✓
- number of pregnancies after the index date; ✓
- use of specific prescribed medications both in the year before the index date and following the index date, confirming the ACS indication: antiplatelet drugs (low-dose acetylsalicylic acid, clopidogrel, dipyridamole, prasugrel, ticlopidine and ticagrelor); ✓
- use of other prescribed medications both in the year before the index date and following the index date: anticoagulants (including dabigatran etexilate and apixaban), antiarrhythmic drugs, antihypertensive drugs, statins, anti-diabetic agents, non-steroidal anti-inflammatory drugs, oral steroids, acid-suppressive drugs, disease-modifying anti-rheumatic drugs, antidepressants, antipsychotic drugs, oral contraceptives, hormone-replacement therapy, strong inhibitors of either cytochrome P450 3A4 or P-glycoprotein (e.g. the systemic azole antimycotics ketoconazole, itraconazole, voriconazole and posaconazole and the HIV-protease inhibitor ritonavir), strong CYP3A4 inducers (e.g. rifampicin, phenytoin, carbamazepine or phenobarbital) and fluconazole; ✓
- renal disease based on diagnoses, most recently recorded before the index date and in following the index date, with estimated glomerular filtration rate (eGFR) or creatinine clearance (CrCl) to be obtained where available; ✓

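### Section 9.1 sets no rule for other anticoagulant use in the ACS comparison, so bleeds on anticoagulant plus antiplatelets count as standard-of-care bleeds and probably bias the ACS bleeding ratio downward

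*Protocol*

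**What the plan says.** Section 9.1 states that "for the secondary prevention of ACS, standard of care is antiplatelet drug(s) such as low-dose acetylsalicylic acid, clopidogrel, dipyridamole, prasugrel, ticlopidine and ticagrelor". A patient enters the ACS comparison through first use of rivaroxaban with antiplatelets, "or use of aspirin and clopidogrel and/or other antiplatelet medications". Neither route carries a condition on other anticoagulants.

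Two exclusions are given. One concerns "Patients who have any record of being prescribed their index drug prior to the enrolment period". The other removes patients who qualify for both cohorts on the same day. A patient who qualifies for both on different days is "assigned to the cohort of drug first prescribed during the enrolment period, with the date of this prescription being the index date". For ACS there is also a waiver on earlier antiplatelet use: "those who have been using one or more platelet inhibitors will remain eligible to enter the study". Earlier anticoagulant use in ACS is not mentioned.

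The protocol's tool for anticoagulant history is the naïve/non-naïve split, with its recent and distant switchers and its check by Read codes and INR values. It is limited to two indications: "Study subjects for DVT/PE treatment and SPAF, where the comparator is warfarin, will be categorized as naïve or non-naïve patients".

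On the analysis side:
- Section 9.3.1 collects "anticoagulants (including dabigatran etexilate and apixaban") in the year before index and after index, in both cohorts.
- Section 9.7.2 defines current use by supply of the index drug and estimates crude rates for DVT/PE treatment, SPAF and ACS.
- Section 9.7.2.1 commits to rate ratios adjusted for age and sex. Adjustment for baseline medication, and the nested case-control analyses, depend on sufficient numbers.
- Table 2 (Section 6) gives crude incidences of the primary safety outcomes in both interim reports.

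**The concern.** In ACS the comparison is rivaroxaban added to antiplatelets against antiplatelets, with bleeding as the primary outcome. If part of the antiplatelet group is also anticoagulated, its bleeding rate is a mixture of two treatments. A higher reference rate lowers the rivaroxaban ratio, which is the non-conservative direction in a safety study.

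This goes beyond detail that a later analysis plan would normally supply. Section 9.1 fixes eligibility and cohort assignment. It considers prior treatment in ACS closely enough to write the platelet-inhibitor waiver, yet sets no rule for the other drug class that bears on the outcome.

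**Working it through.** **1. The plan's own figure.** Section 9.5 asks for 12,000 rivaroxaban and 48,000 warfarin patient-years, at 5 haemorrhagic strokes per 1000 person-years, to exclude a 50% increase with 80% power. Expected events under equal rates are 12,000 × 0.005 = 60 and 48,000 × 0.005 = 240. The standard error of the log ratio is √(1/60 + 1/240) = 0.144, and ln 1.5 = 0.405. With two-sided 5% (assumed, since the protocol states no alpha), power is Φ(0.405/0.144 − 1.96) = 80.2%. The figure reproduces. It concerns warfarin, not the ACS comparator, so here it shows only that a ratio of 1.5 is a size the study treats as important.

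**2. Following patients through Section 9.1.**

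- *Warfarin begun before enrolment; ACS during enrolment, treated with antiplatelets.* The index drug is an antiplatelet, so the warfarin record does not trigger the prior-use exclusion. Without a rivaroxaban prescription, the same-day and first-drug rules do not apply. The naïve/non-naïve flag is not used in ACS. The patient enters the comparator, and a bleed during antiplatelet supply is a standard-of-care bleed.
- *Dabigatran or apixaban, begun at any time.* Neither is an index drug, so the result is the same.
- *Warfarin begun during enrolment, before the ACS.* That prescription already places the patient in the standard-of-care cohort. The protocol does not say whether the patient can enter again as an ACS comparator.
- *Any other anticoagulant begun after an ACS index date.* Person-time still follows antiplatelet supply. Adjustment for baseline medication cannot see the change.

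The gap is therefore clearest for the first, second and fourth patients.

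**3. Size.** Let p be the share of ACS comparator person-time on another anticoagulant, k the bleeding rate ratio of anticoagulant plus antiplatelets against antiplatelets alone, and R the true ratio of rivaroxaban against antiplatelets alone. With no second anticoagulant in the rivaroxaban arm,

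observed ratio = R / (1 + p(k − 1)).

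The documents give neither p nor k; both are assumptions. For R = 1.5:

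| p | k = 1.5 | k = 2 | k = 3 |
|---|---|---|---|
| 2% | 1.49 | 1.47 | 1.44 |
| 5% | 1.46 | 1.43 | 1.36 |
| 10% | 1.43 | 1.36 | 1.25 |
| 20% | 1.36 | 1.25 | 1.07 |

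Over p = 2% to 10% the divisor runs from 1 + 0.02 × 0.5 = 1.01 to 1 + 0.10 × 2 = 1.20, a fall of about 1% to 17%. The 20% row shows the sensitivity beyond that range.

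**4. If the rivaroxaban arm is affected too.** With share q in that arm and the same k, the observed ratio is R(1 + q(k − 1)) / (1 + p(k − 1)). For R = 1.5, p = 5%, k = 2:
- q = 0: 1.43
- q = 2%: 1.46
- q = 5%: 1.50, so the bias cancels
- q = 10%: 1.57, so it reverses

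**5. What would hide a 1.5 entirely.** Setting 1.5 / (1 + p(k − 1)) = 1 gives p = 0.5/(k − 1), which is 50% at k = 2 and 25% at k = 3. Within the assumed range the bias attenuates a signal of that size but does not erase it.

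**The case against.** The strongest reply is that the protocol already has the means to see and handle this. Anticoagulant use is collected in both cohorts. Section 9.7.1 compares co-medication between cohorts by indication, ACS included. Section 9.7.2.1 plans further adjustment and nested case-control analyses where numbers allow, and 9.7.2.7 says biases found in the utilization data can be accounted for in the outcome analyses. Covariate detail is commonly left to an analysis plan.

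This stands in part: an imbalance would probably be noticed. It does not close the gap. The interim rates are crude, the committed ratio adjusts for age and sex only, and baseline adjustment misses later starts. Section 9.1 itself recognises that warfarin users may be identifiable by monitoring codes or INR without a drug code, but attaches that check to a flag that ACS patients do not receive. The covariate in 9.3.1 is prescribed medication, so adjustment could miss the same users.

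Other objections limit what can be claimed:
- A reader might infer that rivaroxaban will certainly look safer in ACS. The documents do not support that. A second anticoagulant should be less common in patients indexed on rivaroxaban, but this is an inference. Patients with both atrial fibrillation and ACS who newly start rivaroxaban with antiplatelets can also fit the ACS assignment wording and could raise the rate in that arm.
- A reader might infer that the same patient can sit in both the ACS comparator and the warfarin comparator. A warfarin user from before enrolment is barred from the latter by the prior-use exclusion. For warfarin begun during enrolment, re-entry is simply not addressed.
- The protocol never says that the ACS reference must be free of anticoagulants, so this is a weakness of design and not a contradiction.
- Section 9.7.2.1 does not say that the adjusted ratio is specific to ACS. A ratio pooled over indications would dilute the effect.

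**Conclusion.** The gap is real. The ACS antiplatelet comparator admits patients on another anticoagulant, mainly those whose anticoagulant began before enrolment or is not an index drug, and their bleeds count as standard-of-care bleeds in the crude rates and in the age- and sex-adjusted ratios.

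The downward direction is likely but conditional: it needs more anticoagulated person-time in the comparator than person-time on a second anticoagulant in the rivaroxaban arm. The 1% to 17% range rests wholly on the assumed p and k and on a rivaroxaban arm without a second anticoagulant. Its lower end is negligible. Its upper end, 1.5 reading as 1.25, matters for a study that takes a 50% increase as the risk to exclude. The change is worth making because the bias is foreseeable, the conditional adjustment does not reliably remove it, and the data needed are already collected.

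**What to change.** In Sections 9.1 and 9.7.2:

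1. Apply the existing anticoagulant-history flag (drug codes, Read codes and INR values) to both ACS groups.
2. Report the ACS rates and ratios with patients on an anticoagulant other than index rivaroxaban at the index date either excluded or shown as a separate stratum. Stratifying keeps every patient and lets the reader see p and q directly.
3. Split or censor person-time in the ACS analysis when another anticoagulant is started during follow-up.

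Two tempting alternatives do not work. Moving these patients to the SPAF or DVT/PE comparison fails for warfarin users from before enrolment, whom the prior-use exclusion bars from the warfarin comparator. A look-back of 6 months alone removes patients who have already stopped and misses those who start after index.

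The cost is a short addition to each section and one flag built from data already collected. The downside is slightly fewer patients, or less person-time, in the main ACS stratum. Exclusion alone would also leave patients with both atrial fibrillation and ACS in the rivaroxaban arm while removing those on another anticoagulant from the comparator, which is a further reason to prefer the stratum.

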9.7.2.7 Sensitivity analyses

Sensitivity analyses will be performed around the start and stop of treatment to account for any differences in the mode of action of rivaroxaban (rapid onset/offset of action, short half-life), warfarin (slow onset/offset of action, long half-life) and other comparators. This will be taken into account in the analyses of outcomes. Analysis of data gathered in the drug utilization/patient characteristics part of the study will allow for the recognition of any unexpected biases, which can subsequently be accounted for in the outcomes analyses.

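### Section 9.1 lets an INR above 2 from the patient's own warfarin start count as prior anticoagulant use, so some new warfarin patients become non-naïve while rivaroxaban patients started the same way stay naïve

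*Protocol*

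**What the plan says.** **Who is naïve.** In Protocol section 9.1, patients treated for DVT/PE or SPAF are classified "according to their previous use of any anticoagulant/comparator drugs". The two definitions are "Naïve patients will be those without a previous prescription recorded before the index date" and "Non-naïve patients will be those with one or more relevant prescriptions recorded before the index date". Which prescriptions are relevant is not defined, and no days before the index date are exempt.

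**Extra evidence.** Status is also to be confirmed from records other than prescriptions. The examples given are "Read Codes for warfarin monitoring, INR values >2, as this may be recorded in the absence of a Drug Code for warfarin". Both are specific to warfarin.

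**Switchers.** Non-naïve patients are divided into recent and distant switchers. Recent switchers are "patients exposed to the other anticoagulant/comparator in the 6 months prior to the index date"; distant switchers had that exposure longer ago.

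**Index date.** Cohort members are "identified using the date of first prescription (index date) of the respective drug (index drug". Section 9.9 lists as a limitation that treatment begun in hospital may not appear in GP notes.

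**Use.** Section 9.3.1 lists the "proportion of patients defined as naïve, non-naïve, recent switchers and distant switchers" among the variables compared between cohorts. Section 9.7.1 stratifies the description and the age- and sex-adjusted odds ratios by naïve and switching status.

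**The concern.** An INR above 2 shows that the patient has been taking warfarin. It does not show whether that was an earlier course or the first days of the present one. In the warfarin cohort the present course is the index drug, so a record from its start says nothing about prior use. Section 9.1 does not make the distinction, and only the warfarin cohort can lose true new starters in this way.

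At stake is a result under the primary objective in section 8.1.1, the description of first-time users. The warfarin cohort would look more pre-treated than it is. The naïve stratum would hold all rivaroxaban patients started in hospital, but only those warfarin patients whose start left no INR or monitoring record before the first GP prescription. Comparisons of comorbidity and co-medication within that stratum would then set differently selected groups side by side.

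**Working it through.** The protocol gives no figure for naïve shares or for records that precede the index date. The study-size figures in section 9.5 do not use naïve status and are not at issue. The check is therefore a reading of the rules, followed by an illustration.

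**Step 1. Apply the rules to two new patients, both started in hospital, with no earlier anticoagulant.**

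| | Warfarin patient | Rivaroxaban patient |
|---|---|---|
| Index date (9.1) | First recorded prescription, which may follow the true start (9.9) | Same |
| Earlier prescription on file | None | None |
| INR above 2 or monitoring code before the index date | Possible, from the index drug itself | Not expected from the index drug; 9.1 names no equivalent marker |
| Status | Non-naïve if such a record exists | Naïve |
| Switcher subgroup | Neither: no exposure to the other drug | Not applicable |

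**Step 2. Look for another rule that would catch the warfarin patient.**
- The section 9.1 exclusion for earlier use of the index drug needs a prescribing record before the enrolment period. This patient has none.
- The 6-month limit only separates recent from distant switchers. It does not protect naïve status.
- The manual review in section 9.7.1 concerns exposure time in a random sample of warfarin users, not naïve status.
- The sensitivity analyses in section 9.7.2.7 concern the start and stop of treatment. They are motivated by differences such as "warfarin (slow onset/offset of action, long half-life", and do not vary the status rule.
- Section 9.7.1 itself proposes INR as the better measure of true warfarin exposure. For this patient that reading points to the index drug, whereas section 9.1 takes the same record as prior use.

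**Step 3. Illustrate the size (all inputs assumed).** Let *t* be the true naïve share, equal in both cohorts. Let *L* and *M* be the shares of truly naïve warfarin and rivaroxaban starters with a record that makes them non-naïve.
- Labelled naïve: warfarin *t*(1 − *L*); rivaroxaban *t*(1 − *M*).
- Share of labelled non-naïve warfarin patients who are really new: *tL* / [1 − *t*(1 − *L*)].
- Spurious odds ratio for non-naïve status, warfarin against rivaroxaban: the odds of being labelled non-naïve in the warfarin cohort divided by those in the rivaroxaban cohort.

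Example with *t* = 0.8, *L* = 0.3, *M* = 0: warfarin naïve 0.8 × 0.7 = 0.56; really new 0.24/0.44 = 55%; odds ratio (0.44/0.56)/(0.20/0.80) = 3.14.

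| *t* | *L* | *M* | Labelled naïve, warfarin | Non-naïve but really new | Spurious odds ratio |
|---|---|---|---|---|---|
| 0.6 | 0.1 | 0 | 0.54 | 13% | 1.28 |
| 0.6 | 0.3 | 0 | 0.42 | 31% | 2.07 |
| 0.6 | 0.5 | 0 | 0.30 | 43% | 3.50 |
| 0.8 | 0.1 | 0 | 0.72 | 29% | 1.56 |
| 0.8 | 0.3 | 0 | 0.56 | 55% | 3.14 |
| 0.8 | 0.5 | 0 | 0.40 | 67% | 6.00 |
| 0.8 | 0.3 | 0.3 | 0.56 | 55% | 1.00 |

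For the INR route *M* = 0 is the natural case, because the named markers cannot come from rivaroxaban. The true *L* may lie below 10%; at *L* = 0 there is no distortion. The last row shows that equal rates in the two cohorts leave the odds ratio at 1.00.

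**The case against.** **The INR rule is a sensible safeguard.** A patient with an INR above 2 before the first GP prescription was already anticoagulated, and a new-user analysis has reason to set such patients apart. In the rivaroxaban cohort the check also finds switchers whose warfarin was never coded. That second purpose stands, and the fix must keep it. The first argument is weaker. A rivaroxaban patient started in hospital is equally past the start of treatment and stays naïve, so the safeguard works on one side only.

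**The wording is loose, and detail may follow elsewhere.** INR above 2 is given as an example, the check is described as confirmation, and Figure 1 is not legible in the text at hand. However, the stated reason for the check is that warfarin use can be on file without a drug code, so it is meant to change status where prescriptions are silent. Section 9.1 fixes the definition, and its switcher subgroups leave this patient unplaced.

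**Stronger readings that the protocol does not support.**
- A reader might infer that another anticoagulant prescribed alongside a slow-acting drug makes new warfarin patients in general non-naïve. The protocol does not say that such a drug is given or how often. The prescription rule is also the same in both cohorts, so a rivaroxaban starter with an earlier prescription of another anticoagulant becomes non-naïve too.
- A reader might infer bias in the bleeding comparison. If a fraction *q* of warfarin starters left the naïve group and bled *k* times as often as those who stayed, a true naïve-only ratio of 1.0 would read 1 + *q*(*k* − 1). That is 1.02 at *q* = 0.1, *k* = 1.2 and 1.25 at *q* = 0.5, *k* = 1.5. Both inputs are assumed, *k* below 1 reverses the direction, and sections 9.7.2.1 to 9.7.2.4 name no outcome rate ratio stratified by naïve status.

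**Conclusion.** The concern holds for INR and monitoring records. As written, section 9.1 can label a new warfarin patient non-naïve on evidence of the index drug itself, leaves that patient outside both switcher subgroups, and has no counterpart for rivaroxaban. The misclassification is differential.

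Its reach is limited to the reported naïve and non-naïve proportions and the drug-utilization odds ratios stratified by status, for DVT/PE treatment and SPAF. Results that are overall or stratified by indication alone are untouched. Only warfarin patients with such a record before their first recorded prescription are affected.

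The size is unknown. The range of 1.28 to 6.0 rests on an assumed true naïve share of 60% to 80%, an assumed 10% to 50% of new warfarin starters with such a record, and none among rivaroxaban starters. It shows that the effect need not be small; it is not an estimate.

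**What to change.** Add to section 9.1:

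- In the warfarin cohort, monitoring codes and INR values dated on or after the qualifying diagnosis, and within a short fixed window (for example 30 days) before the first recorded warfarin prescription, count as the start of the index drug. They do not by themselves make the patient non-naïve.
- In the rivaroxaban cohort, such records remain evidence of a recent switch from warfarin. Exempting them in both cohorts would relabel real switchers as naïve and contradict the protocol's own 6-month definition.
- State which prescriptions are relevant. Keep the stated rule in both cohorts for prescriptions of another anticoagulant in the same window, and add a sensitivity table by type of prior drug. Section 9.3.1 already collects this for non-naïve patients.

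Report the number of warfarin patients whose status changes, and repeat the stratified tables with status set by drug codes only.

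The cost is a short definition, one date comparison and a few extra tables from data already planned. The downside is that a few warfarin patients with genuine but unrecorded earlier use close to the index date may be counted as naïve. Varying the window (for example 14, 30 and 60 days) shows how much this matters.

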9.7.1 Patient characteristics and drug utilization

The patient populations will be described according to the descriptive variables mentioned in Section 9.3.1. overall and stratified by indication (VTE prevention, DVT/PE treatment, SPAF, ACS, other), naïve or non-naïve status, and switching status.

The baseline risk of being dispensed one of the co-medications or presenting with one of the comorbidities prior to the index date will be assessed by computing the odds ratio of being prescribed that drug or presenting with that comorbidity among first-time users of rivaroxaban compared with first-time users of standard of care. Age- and sex-adjusted odds ratios and 95% confidence intervals for the descriptive variables ([Section 9.3.1](#)), will be computed using logistic regression models both overall and stratified by indication and by naïve or non-naïve status, and switching status.

Manual review of patient profiles will be used to ascertain as accurately as possible exposure time in a random sample of warfarin users. In addition, INR measurements will be used as a proxy for warfarin exposure, which is more valid measure of true exposure to warfarin.

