9.9 Limitations of the research methods

Limitations of this study include:

- The possibility for unmeasured confounders for bleeding affecting the data e.g. inadequate or missing recording of ethnicity, alcohol intake or over-the-counter use of some medications.
- Potential for misclassification of exposure to warfarin due to complex dosing with multiple strengths of tablet.
- Prescriptions started in-hospital or events in the immediate post-discharge period may be missed from general practitioner notes.
- Incomplete data concerning medication compliance: drug use is based on prescriptions written by the treating physician, but no information is available to confirm if the drug was actually taken by the patient.

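### Monitoring codes and INR values above 2 count as evidence of earlier warfarin use for the naïve label but not for eligibility, so prior warfarin users can enter the first-time warfarin cohort

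*Protocol*

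**What the plan says.** Section 9.1 admits a patient as a first-time user "when he or she has a first prescription of the drug recorded during the enrolment period". It excludes "Patients who have any record of being prescribed their index drug prior to the enrolment period". Neither rule mentions monitoring codes or INR.

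For DVT/PE treatment and SPAF, the same section then sorts the admitted patients: "Ascertainment of naïve/non-naïve status will also be confirmed by Read Code in addition to Drug Codes". The examples given are Read codes for warfarin monitoring and "INR values >2, as this may be recorded in the absence of a Drug Code for warfarin". Non-naïve patients stay in the cohort and are split by time since exposure to the other drug. The nearer group is "recent switchers (patients exposed to the other anticoagulant/comparator in the 6 months prior to the index date"; the distant group is defined the same way beyond 6 months.

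INR has one further use. Section 9.7.1 says "INR measurements will be used as a proxy for warfarin exposure, which is more valid measure of true exposure to warfarin". That concerns exposure, not eligibility. Section 9.9 lists as a limitation: "Prescriptions started in-hospital or events in the immediate post-discharge period may be missed from general practitioner notes".

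Section 9.7.1 stratifies the baseline description and its odds ratios by naïve and switching status. Section 9.7.2.1 plans age- and sex-adjusted Poisson rate ratios for the primary outcomes. Further adjustment is made only if numbers and data allow, and naïve status is not named.

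**The concern.** The protocol sets out to compare new users with new users. For warfarin it concedes that a prescription record is an incomplete marker of use and calls INR the more valid measure of exposure. Yet the less complete marker alone decides who counts as a first-time user.

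Take a patient whose warfarin was managed by a clinic for years, with INR results on file and a first primary-care prescription during enrolment. The entry rule is met and the exclusion as worded does not apply. The patient is in the first-time warfarin cohort, labelled non-naïve. The text then gives no subgroup, because the prior exposure was to warfarin itself.

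This does not look like a deliberate allowance. Where the protocol wants to keep prior users (platelet inhibitors in ACS), section 9.1 says so and gives a reason. It gives none for warfarin.

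At stake is the comparator rate in the primary rate ratios. Patients already past the start of treatment have survived any early high-risk period. If that period carries more bleeding, they lower the warfarin rate and raise the ratio.

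**Working it through.** **1. Rules set side by side**

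| Decision | Evidence named in the protocol |
|---|---|
| Entry to cohort (9.1) | First recorded prescription in the enrolment period |
| Prior-use exclusion (9.1) | Record of being prescribed the index drug before enrolment |
| Naïve or non-naïve (9.1) | Drug codes plus monitoring Read codes and INR above 2 |
| Warfarin exposure (9.7.1) | INR as proxy; profile review in a random sample |

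A patient with INR above 2 but no warfarin drug code before enrolment, and a first drug code during it, passes the first two rows and is caught only in the third.

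**2. The plan's own study size**

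Inputs from 9.5: 5 events per 1000 person-years, 12,000 and 48,000 person-years, ratio to exclude 1.5, power 80%. Two-sided 5% is assumed, as alpha is not stated.

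- Events: 12,000 × 0.005 = 60 and 48,000 × 0.005 = 240.
- SE of log ratio = √(1/60 + 1/240) = 0.1443.
- Power = Φ(ln 1.5/0.1443 − 1.96) = Φ(0.849) = 80.2%.

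The figure reproduces, so the point does not touch the study-size arithmetic.

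**3. Possible size of the distortion (assumed inputs)**

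Let D be years of current use, R the bleeding rate in the first 90 days (0.25 year) relative to later, and f the share of warfarin person-time from prior users at the later rate. The true ratio is 1 and all rivaroxaban users carry the new-user rate.

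- New-user mean rate M = [0.25R + (D − 0.25)]/D
- Apparent ratio = M / [(1 − f)M + f]

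| D | R | M | f | Apparent ratio |
|---|---|---|---|---|
| 3 years | 2 | 1.083 | 10%, 20% | 1.008, 1.016 |
| 1 year | 2 | 1.25 | 10%, 20% | 1.25/1.225 = 1.02; 1.25/1.20 = 1.04 |
| 6 months | 3 | 2.0 | 10%, 20%, 30% | 2/1.9 = 1.05; 2/1.8 = 1.11; 2/1.7 = 1.18 |

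**4. Offset from rivaroxaban switchers**

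If a share g of rivaroxaban person-time also comes from patients past the early period, the numerator becomes (1 − g)M + g. With D = 1, R = 2, f = 20%: g = 10% gives 1.225/1.20 = 1.02, and g = 20% gives 1.20/1.20 = 1.00. If g exceeds f, the ratio falls below 1. This assumes that the early excess belongs to starting any anticoagulant.

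**5. Effect on power to exclude 1.5**

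Here k is the prior users' rate relative to new users. The apparent ratio is 1/[(1 − f) + fk], and warfarin events fall to 240 × [(1 − f) + fk].

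- f = 10%, k = 0.7: ratio 1/0.97 = 1.03, power 74%.
- f = 20%, k = 0.5: ratio 1/0.90 = 1.11, power 54%.

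Removing those patients instead leaves 240 × (1 − f) warfarin events. For f = 5%, 10%, 20% and 30%, power is 79.8%, 79.4%, 78.3% and 76.9%.

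**The case against.** The strongest reply is that these patients are flagged, not hidden. Naïve status is a collected variable (9.3.1), it stratifies the baseline comparison (9.7.1), and 9.7.2.7 says that biases seen in the utilization data can be accounted for in the outcome analyses. A separate analysis plan might restrict to naïve patients. That is fair, but it does not mend the eligibility rule: the protocol's stated primary ratios include these patients.

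The exclusion wording could also be read more widely than drug codes. It could, but section 9.1 names monitoring codes and INR only for the label, so two programmers could build different cohorts.

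Several stronger readings are tempting and not supported:

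- *Prior users certainly enter in material numbers.* The text shows only that they can. Clinic-managed patients who never receive a primary-care prescription never enter, and no share is given.
- *INR above 2 proves earlier warfarin use.* It is strong evidence, not proof; warfarin is described only as the most widely used vitamin K antagonist.
- *The ratio is biased against rivaroxaban.* Switchers kept in the rivaroxaban cohort may also have passed the early period, so the net direction is not established.
- *A hospital-started warfarin patient with one INR shortly before the first prescription is definitely misclassified.* The protocol offers the INR rule as an example of confirmation and does not fix that outcome.
- *No class exists at all for these patients.* The text provides none, but Figure 1 is not available here and may show a further branch.

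**Conclusion.** The point stands as an inconsistency in the eligibility logic. The protocol recognises non-prescription evidence of warfarin use, applies it to a label and withholds it from the exclusion that defines a new user.

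Under assumed inputs the ratio could be inflated by roughly 1% to 18%. The upper end needs 6 months of use, a three-fold early rate and 30% prior users together. The one-year, two-fold case with 10–20% prior users gives 2–4%, against a margin of 50%. These figures assume higher early bleeding and no offset from rivaroxaban switchers; the documents quantify neither, nor the share of prior users. A reader might infer a demonstrated bias in the primary result, but the documents support only a route by which one can arise.

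The change is still worth making: it serves the stated new-user comparison, and removing up to 30% of warfarin person-time costs only about 3 points of power.

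**What to change.** Amend section 9.1 as follows.

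- Apply the monitoring-code and INR above 2 evidence to the prior-use exclusion for the warfarin cohort.
- Pre-specify a window before the first warfarin prescription, for example 30 days, inside which such evidence counts as the same treatment start and does not by itself make the patient non-naïve. The documents give no basis for a particular length, so vary it in a sensitivity analysis.
- Keep the index date at the first prescription, so that no immortal time is created.
- In the warfarin cohort, reserve the non-naïve label for prior use of another anticoagulant, so that it agrees with the switcher definitions.
- Add to section 9.9 that hospital-started rivaroxaban leaves no equivalent marker, so ascertainment of earlier use differs between cohorts.

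The cost is protocol wording and a change to the cohort-entry program. The codes and INR values are already to be used, and 9.2 requires at least a year of registration for every patient. The warfarin cohort becomes somewhat smaller. Two imperfections remain: patients inside the window have already passed some early treatment time, and part of the hospital-start asymmetry persists.
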